Xpert MTB/RIF	molecular assay by Cepheid for the rapid detection of tuberculosis and rifampin resistance
URBAN-ARCH	Uganda Russia Boston Alcohol Network for Alcohol Research on HIV/AIDS
WHO	World Health Organization

1. Study Synopsis

TB is the leading cause of death among persons with HIV worldwide. Globally, approximately 25% of persons with HIV are heavy drinkers, and heavy alcohol use is associated with a 3-fold higher risk of TB disease compared to no alcohol use, thus HIV-infected persons who drink alcohol are at high risk for TB. Six months of isoniazid (INH) preventive therapy (IPT) reduces TB incidence and mortality by 30-50% above the positive impact of antiretroviral therapy (ART). However, INH can be toxic to the liver, and thus many heavy alcohol users in resource-limited settings such as east Africa are not offered IPT. In addition, heavy alcohol users have poorer ART adherence and data suggest decreased IPT adherence as well. Thus interventions are needed to both decrease alcohol use and increase IPT adherence, and thereby reduce INH toxicity, TB morbidity and mortality in this high-risk population. The use of incentives to promote healthy behavior has been shown to be a highly effective approach for reducing substance use and for improving adherence to HIV and TB regimens in high-income countries. Reducing alcohol use may create a window for safe and effective IPT use by decreasing hepatotoxicity and increasing IPT adherence; however, additional interventions for IPT adherence may be needed. The use of incentives conditional on reduced alcohol use or increased INH adherence in resource-limited settings has been previously limited by the lack of reliable, rapid tests for these behaviors. Recent technological advances allow for point of care (POC) urine testing for recent alcohol use with an ethyl glucuronide (EtG) dipstick that is positive for 3 days after heavy drinking, and INH pill-taking using the IsoScreen urine test to test for 24-hour INH ingestion, thereby creating an opportunity to test incentive-based interventions during IPT among heavy drinkers. We propose leveraging two established cohorts of persons with HIV in Uganda for a randomized 2x2 factorial trial among HIV/TB co-infected adults with heavy alcohol use (n=680 persons. 340 each U01 cohort). **Aim 1** is to determine whether economic incentives contingent on reduced alcohol use assessed by POC EtG tests conducted at INH refill visits reduces heavy alcohol use over six months of IPT compared to the control. **Aim 2** is to determine whether economic incentives contingent on INH positive POC urine tests at these visits compared to the control increases IPT adherence over six months. **Aim 3** is to examine the longer-term impact of the intervention on HIV virologic suppression, and examine mediators of an effect. Primary outcomes will be self-reported heavy alcohol use augmented by phosphatidylethanol (PEth) concentrations, and INH adherence, measured using medication event monitoring system (MEMS), with additional measurements of pill ingestion by INH levels in hair samples. Using incentive-based interventions to reduce alcohol use and increase medication safety in low-income settings is novel. This study to optimize IPT in HIV/TB co-infected drinkers will provide new information on low-cost strategies to reduce alcohol use and increase IPT adherence in low-income countries.

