2.1. Specific Aims

Aim 1: Determine the effectiveness of economic incentives contingent on point-of-care (POC) urine ethyl glucuronide (EtG) <300 ng/mL (Arms 2 & 4) versus no alcohol incentives (Arms 1 & 3) to reduce heavy drinking over 6 months, among HIV/TB co-infected adult drinkers receiving IPT. We will randomize participants to low-cost escalating prize incentives for EtG negative urine tests at IPT refill visits (Arms 2+4), versus no incentives (Arms 1+3).

- Hypothesis: Incentives will be more effective in promoting decreased alcohol use during IPT versus the control, resulting in less hepatotoxicity and greater IPT adherence in the intervention versus the control group.
- Outcomes: Primary: Non-heavy drinking determined by self-report (Alcohol Use Disorders Identification Test – Consumption [AUDIT-C], prior 3 months, negative) *and* phosphatidylethanol (PEth) <35 ng/mL at three *and* six months. Secondary: IPT adherence and hepatotoxicity.

Aim 2: Determine the effectiveness of economic incentives contingent on POC (IsoScreen) INH urine positive tests (Arms 3 & 4) versus no INH incentives (Arms 1 & 2) on INH adherence among HIV/TB co-infected adult drinkers. We will randomize participants to low-cost escalating prize incentives for INH positive urine tests at IPT refill visits (Arms 3+4), versus no incentives (Arms 1+2).

- Hypothesis: The incentive strategy will result in greater INH adherence versus the control.
- Outcomes: Primary: INH adherence measured as >90% pill-taking days by medication event monitoring system (MEMS) cap opening over six months. Secondary: INH concentration in hair at 3 and 6 months.

Aim 3: Assess the impact of economic incentives on HIV virologic suppression and explore their mechanisms of action, six months after trial completion. We will follow all study participants for six months after trial completion.

a) **Assess the impact of the 3 separate incentive interventions (Arms 2,3,4) vs. no incentives (Arm 1) on HIV virologic suppression.**

- Hypothesis: The intervention arms will be associated with greater viral suppression versus control.
- Outcomes: Primary: The proportion with undetectable HIV viral load six months post-IPT completion. Secondary: Active TB rates six months after IPT completion.

b) **Explore the mechanisms that may drive the economic incentives to increase virologic suppression.**
Potential mediators will be reductions in alcohol use and level of IPT adherence.

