4.1. Study setting

[figure not shown]
The DIPT study will take place in southwestern Uganda, where the adult HIV prevalence is 8%¹³⁶ and TB infection prevalence is estimated at 28-50%.^{137,138} Heavy alcohol use is common while other substance use is rare.¹³⁹ This is an appropriate setting for this intervention, because trials conducted in settings across Africa with similar HIV and TB prevalence have demonstrated that 6 months of IPT is effective in decreasing active TB incidence and mortality,^{3,140} in contrast to settings in southern Africa which have very high TB transmission and where longer durations of IPT may be needed.^{141,142} We will leverage the existing Uganda URBAN ARCH and SEARCH HIV clinical cohorts; each cohort will enroll 340 patients and up to 5 pilot participants.

The DIPT 1/2 cohort will be based at the Immune Suppression Syndrome (ISS) HIV Clinic of the Mbarara Regional Referral Hospital (MRRH), the site of the Uganda URBAN ARCH cohort, and its affiliate clinic, the Mbarara Municipality Clinic. There are over 12,000 active patients at the ISS Clinic; 25% are current drinkers.¹⁴³ The ISS Clinic and pharmacy use electronic medical records (EMR) that will be leveraged for patient recruitment, tracking, and active TB outcomes.

The DIPT 2/2 cohort will be enrolled from the 10 HIV clinics in southwestern Uganda taking part in the SEARCH study. Each SEARCH community is within the catchment area of a government and PEPFAR-supported ART clinic. In southwestern Uganda, >10,000 HIV+ adults are on ART at these 10 clinics, providing an ample population base for DIPT 2/2 enrollment. Among HIV+ SEARCH participants in southwestern Uganda, 27% are current drinkers. SEARCH has digitized medical records at these 10 clinics, including data on alcohol use and TB disease surveillance; this infrastructure will be leveraged for patient recruitment, tracking and HIV and TB outcomes in DIPT 2/2. Recruitment may also occur at additional HIV clinics in Southwestern Uganda as needed to meet study target enrollment.

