5.5. Study visits

As previously described, eligibility will be a two-stage process in order to determine drinking status, TST status, and rule out active TB and liver enzyme elevations. Baseline visits will include collection of tracking information, a baseline survey (Table 2), blood draw, and repeat liver enzyme testing if it has been longer than one month from the screening tests.

[figure not shown]
Visits for INH refills and assessments for toxicity (assessment of side effects and liver enzyme testing) will occur at week 2 and months 1 through 6 for all study participants. Urine will be collected and prizes administered as described above for Arms 2, 3, and 4. Hair collection will occur at 3 and 6 months c at the time of the INH discontinuation if outside of the 3- and 6-month time point for all study participants (see below). Follow-up interviews and blood collection will occur at months 3, 6, and 12 (Table 2). Screening for symptoms of active TB, and sputum testing and chest X-ray if symptoms are reported, will occur at every follow-up visit.

Arms 2-4 only: Urine test(s) and prize(s)
↓
Month 12: Study survey, Blood draw (PEth, VL)

Retention: High retention (90% at six months, 85% at one year) will be maintained as in our prior studies using follow-up phone calls, alerts when patients come to their home clinic, and home visits when needed. To encourage high retention, participants in all study arms, including control, will receive travel reimbursements (low-value unconditional cash transfers) of up to US\$5 for attending study visits (see Figure 3).

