5.9.3. Aim 3a analyses

We will use multiple logistic regression models including variables to represent the study arms and will also adjust for gender and study site (randomization stratification factors) to improve efficiency, as in Aims 1 & 2. The 3 pairwise comparisons of primary interest are between each intervention (Arms 2, 3, and 4) vs. control (Arm 1) and we will adjust for the multiple comparisons using the Hochberg sequential test procedure.¹⁸⁵ A secondary outcome of interest is virologic suppression at trial completion, analyzed using the same approach as above.

Statistical power: We expect 15% loss to follow-up at 6 months post-trial. We assume a conservative analysis based on a Bonferroni adjustment for multiple comparisons. For an overall type I error rate of 5%, we assume each of the 3 pairwise comparisons will be conducted at an alpha level of 0.0167. We expect that 67% of participants in the control group will have viral suppression at 6 months post-trial (SEARCH data). Given this assumption, the proposed study has 80% power to detect an absolute difference of 17% in the proportions with undetectable viral load for any of the 3 comparisons of interest (e.g., 84% vs. 67% in Arms 2,3, and 4 versus Arm 1, respectively) using a chi-square test with continuity correction.

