5.9.5. Additional analyses

Intervention effects over time. For Aims 1 & 2, we will conduct secondary analyses to assess intervention effects separately at 3 and 6 months and to assess for possible intervention by time interactions. We will use generalized linear mixed effects models that include subject-specific random intercepts and slopes for continuous outcomes and generalized estimating equations (GEE), with an independence working correlation matrix and logit link for dichotomous outcomes. Additional analyses will also be performed using mixed effects logistic regression models for correlated binary outcomes.

Moderators. We will perform additional analyses to explore potential moderators of the incentive interventions. For Aims 1 and 2, the potential moderators of interest are: sex, baseline level of alcohol use, readiness to change, and discount rate. Although we do not expect interaction between the two interventions, we will assess and test this as well. For each aim, we will fit separate models including 2-way interactions between randomization group and each potential effect moderator, as well as a model testing the interaction between the two interventions. If an interaction is significant, subsequent stratified analyses will be conducted to explore the effect of the economic incentives intervention by categories of the moderator.

Missing data. Participants who meet eligibility criteria and enroll in the study will be compared with eligible participants who decline enrollment, using the 2 independent samples *t*-test and Fisher's exact test. We will similarly test for differences between participants lost to follow-up and those who complete the study. In addition, data collected to the point of lost to follow-up will be compared to the data of those who complete the study to examine missing data mechanisms. In situations where missing data occurs, we will document the reasons for the missing data whenever possible. If it is reasonable to assume that data are missing at random, multiple model based imputation methods^{193,194} will be applied if needed.

6. Safety considerations

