The primary outcome for Aim 2 (i.e., to estimate the effect of incentives contingent on a positive IsoScreen test) will be INH adherence measured as >90% pill-taking days by MEMS cap opening during the six-month course of INH or the time prescribed for those who were instructed to discontinue INH, a binary variable. The participants were given up to 9 months to complete a 6-month (180-pill) INH preventive therapy course. Therefore, MEMS adherence is defined as the number of pill bottle openings (no more than 1 per day counted) within a 270-day window divided by the number of prescribed doses (180, unless the participant discontinued the medication).

The outcome for Aim 3 is treated as a secondary outcome (see below).

Secondary outcomes

The secondary outcome for Aim 1 is PEth as a continuous variable measured at the 6-month visit.

The secondary outcome for Aim 2 is MEMS-measured adherence as a continuous variable (defined as the proportion of days with a bottle opening out of number of days prescribed within 9 months of randomization).

The outcome of Aim 3 is HIV virological suppression defined as an undetectable plasma HIV viral load at the 12-month visit (a binary variable). Another secondary outcome for Aim 3 will be HIV virological suppression at the 6-month visit (a binary variable).

Another secondary outcome is INH preventive therapy discontinuation due to grade 3 or grade 4 hepatotoxicity at any time while receiving INH (a binary outcome). Grade 3 hepatotoxicity was defined as AST or ALT ≥ 5 ULN or based on symptoms that met pre-specified Grade 3 criteria for hepatotoxicity. Grade 4 hepatotoxicity was defined as AST or ALT ≥ 10 ULN or based on symptoms that met pre-specified Grade 4 criteria for hepatotoxicity.

Finally, active TB during the 12 months of follow-up (a binary outcome) is also a secondary outcome. Active TB is defined as confirmed (if Xpert MTB/RIF assay positive) or suspected (based on chest x-ray findings or response to anti-TB treatment in a symptomatic and Xpert assay negative person).

Descriptive statistics

We will report the distribution of baseline covariates overall and by randomization arm. For continuous variables, we will provide the median, mean, standard deviation, 0th, 25th, 50th, 75th, and 100th percentiles. For categorical variables, we will provide frequencies and proportions. Differences between arms will not be evaluated based on statistical significance.

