Analyses of the secondary outcomes

For the hepatotoxicity outcome, we will use a logistic regression model including indicator variables to represent the study arms and, to improve efficiency, the randomization stratification factors (gender and study site). We will conduct 3 pairwise comparisons between each intervention (Arms 2, 3, and 4) versus the control (Arm 1).

For all other binary secondary outcomes, we will use the same statistical approach we described for the primary outcomes including a factorial analysis and a test for interaction between the interventions.

If the statistical analyses indicate an effect of the alcohol intervention versus no alcohol intervention on HIV virological suppression, we will then conduct a mediation analysis to explore the role of alcohol drinking as a potential mediator that may drive the intervention to improve HIV virologic suppression. Similarly, if the statistical analyses indicate an effect of the INH adherence intervention versus no INH adherence intervention on HIV virological suppression, we will then conduct a mediation analysis to explore the role of INH adherence as a potential mediator that may drive the intervention to improve HIV virologic suppression. More specifically, we will use methods for mediation analysis to derive the direct and indirect effects of the incentives for the primary outcomes while allowing for exposure-mediator interactions[7, 8]. We will specify a priori the list of mediator-outcome confounders.

For all continuous secondary outcomes, we will fit linear regression models. We will explore transformations for variables that are not normally distributed. If an appropriate transformation is not identified, median regression will be used. For the continuous alcohol outcomes, we will also adjust the models for the baseline drinking variables (analysis of covariance).

For all secondary outcomes, we will declare statistical significance if the p-value is < 0.05.

Missing data. For all secondary analyses we will conduct a complete case analysis.

Exploratory analyses

Exploratory outcomes. Exploratory outcomes for Aim 1 are the following continuous measures of drinking: 1) self-reported number of drinking days in the prior 30 days, 2) number of heavy drinking days (defined as ≥ 4 drinks/occasion and ≥ 5 drinks/occasion for women and men, respectively) in the prior 14 days, and 3) PEth as a continuous variable measured at other time points.

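### The SAP analyses every secondary outcome by complete case with no sensitivity analysis, including month-12 viral suppression, where 15% loss is expected and earlier viral loads are held

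*SAP*

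**What the plan says.** SAP, Analyses of the secondary outcomes, Missing data: "For all secondary analyses we will conduct a complete case analysis". No condition or sensitivity analysis follows. Three further steps appear only under the SAP's primary outcomes: a comparison of participants with and without outcome data, an analysis counting missed visits as heavy drinking, and weighting to be considered if more than 10% is missing.

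Month-12 viral suppression is the primary outcome of Aim 3 in Protocol 5.7.1. The SAP lists it as secondary, which is how it falls under this rule. Protocol 5.9.3 states "We expect 15% loss to follow-up at 6 months post-trial", and 5.5 sets the same 85% one-year retention target. Protocol Table 2 schedules viral load at eligibility, month 6 and month 12.

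Protocol 5.9.5 says that "multiple model based imputation methods" will be applied if needed when missing at random is reasonable, and that those lost will be compared with completers. Protocol 4.1 names clinic records for TB outcomes in both cohorts, but for HIV outcomes only in one: "tracking and HIV and TB outcomes in DIPT 2/2".

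For TB, the SAP says "active TB during the 12 months of follow-up (a binary outcome) is also a secondary outcome". Protocol 5.5 screens for TB symptoms at every follow-up visit.

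**The concern.** The Aim 3 power calculation allows for the precision lost to 15% attrition. It does not address bias, and the SAP plans nothing for this outcome that would reveal it.

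Informative loss is plausible on the documents' own account. The SAP calls it reasonable to treat those who miss month 3 or 6 as drinking heavily, and Protocol section 3 cites an adjusted odds ratio of 1.62 for detectable viremia with binge drinking. Loss could also differ by arm: the trial is open label, and only Arms 2 to 4 can win prizes at refill visits. An apparent effect on suppression also triggers the SAP's mediation analysis, so a retention artefact would carry forward.

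For active TB, the SAP does not say who counts as a complete case over 12 months. It is therefore unclear how someone last screened TB-free at, say, month 6 is handled.

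**Working it through.** **Inputs from the documents.** 680 participants ("n=680 persons. 340 each U01 cohort"), allocation 1:1:1:1, 15% loss at month 12, control suppression 67%, alpha 0.0167 per pairwise comparison in the protocol (taken as two-sided, as stated for Aim 1), p < 0.05 for secondary outcomes in the SAP.

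**The plan's own figure.** Evaluable per arm: 680 × 0.85 / 4 = 144.5. For 84% v 67% with continuity correction, 80% power needs 145 per arm; power at 144.5 is 80.1%. The stated 80% reproduces.

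**Detectable difference under the SAP.** The SAP uses a factorial contrast for this outcome: 680 × 0.85 / 2 = 289 per group. At two-sided 0.05, with continuity correction and 67% in controls, 80% power is reached at about 10.8 points.

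**Amount missing.** 680 × 0.15 = 102, above the 10% level at which the SAP would consider weighting a primary outcome.

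**Bias with no true effect.** Let p = 67% be true suppression in both groups, L the loss and q the suppression among those lost. Then

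- complete case: (p − L·q) / (1 − L)
- missing counted as not suppressed: p − L·q

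The values of L by group and of q are assumptions. Average loss is 15% throughout. Differences are intervention minus control; type I error uses 340 v 340 randomised, two-sided 0.05, normal approximation.

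| Loss, control v intervention | q | Complete case, control v intervention | False difference | Type I error | Missing as not suppressed |
|---|---|---|---|---|---|
| 15% v 15% | 30% or 50%, same in both | equal | 0 | 5% | 0 |
| 18% v 12% | 50% | 70.73% v 69.32% | −1.4 | 6.6% | +3.0 |
| 18% v 12% | 30% | 75.12% v 72.05% | −3.1 | 13.4% | +1.8 |
| 20% v 10% | 50% | 71.25% v 68.89% | −2.4 | 9.5% | +5.0 |
| 20% v 10% | 30% | 76.25% v 71.11% | −5.1 | 29% | +3.0 |
| 15% v 15% | 50% v 30% | 70.00% v 73.53% | +3.5 | about 16% | +3.0 |

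Example, fifth row: (0.67 − 0.20 × 0.30) / 0.80 = 0.7625 and (0.67 − 0.10 × 0.30) / 0.90 = 0.7111.

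If the intervention group lost more, the signs in the unequal-loss rows would reverse. In those rows, counting missing as not suppressed errs in the opposite direction to complete case. In the last row both err the same way, so the two do not always bracket the truth.

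**The case against.** The strongest reply is that the harm is conditional. Neither loss by arm nor suppression among those lost is in the documents, loss to the study is not loss to HIV care, and the first row of the table shows no bias. The protocol's comparison of those lost with completers is not withdrawn, and its imputation clause was itself conditional. All of this stands. It limits the claim to a possibility that the SAP should be able to examine; it does not supply the missing analysis. Nor does the SAP's statement that other binary secondary outcomes follow the primary approach import the primary missing-data steps, because an explicit complete-case rule follows it.

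Several stronger readings are tempting but unsupported:

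- **That the SAP abandoned a TB rate analysis.** Protocol 2.1 does write "Active TB rates six months after IPT completion", but Protocol 5.7.1 defines the outcome as active TB at any time in the 12 months after enrollment, matching the SAP.
- **That complete case must overstate TB risk by a fixed amount.** This depends on when loss occurs and on an undefined complete-case rule. Assume a true 3% risk, 15% loss, and removal of those lost while TB-free. Loss at entry with equal risk gives 0.0255 / 0.85 = 3.0%, no bias. Constant hazard with loss at month 6 gives (0.0255 + 0.15 × 0.015) / (0.85 + 0.15 × 0.015) = about 3.26%.
- **That nothing draws participants to month 12.** Protocol 5.5 gives all arms travel reimbursement for study visits, plus calls and home visits. Only the arm-specific prizes end, which weakens the case for unequal loss at that visit.
- **That clinic records would fill the gaps.** HIV records are named for DIPT 2/2 only, and no clinic viral load is scheduled for those who miss month 12.
- **That month-3 PEth is ignored.** The SAP's exploratory section plans random-effect models for continuous outcomes across months 3 and 6.

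**Conclusion.** The concern holds as an inexpensive improvement to the SAP. The outcome that carries Aim 3 has about 102 expected missing values, earlier viral loads that could inform them, and one unconditional complete-case rule with no check. The protocol's conditional imputation clause and the SAP's rule need reconciling.

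Under the unequal-loss assumptions, the false difference is about 1.4 to 5.1 points, roughly an eighth to just under half of the 10.8 points detectable, with type I error of 6.6% to 29%. This range illustrates what could happen; it does not predict bias in this trial. Unequal loss alone is not enough: suppression among those lost must differ from that among those retained. Equal loss can also mislead if that relation differs by arm. For active TB, the conclusion is only that the complete-case rule is undefined and that censoring would use the visit data better; no size is claimed.

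**What to change.** **Month-12 viral suppression.** Keep complete case if wished, and add multiple imputation (or inverse probability weighting) using arm, gender, site, and eligibility and month-6 viral load. Show loss by arm. Report the analysis counting missing as not suppressed only beside this, as one extreme, noting that under unequal loss it can err in the opposite direction to complete case. Use clinic viral loads only where they exist, and say for which cohort.

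**Active TB.** Analyse time to TB or cumulative incidence to 12 months, censoring at the last TB screen or clinic record, so that people lost while TB-free contribute their follow-up. State whether record-based diagnoses count.

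**PEth.** A joint month-3 and month-6 model for the month-6 estimate is optional.

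**Cost.** SAP wording and modest programming. Imputation and weighting rest on missing at random given the variables used, and the TB analysis assumes that loss is unrelated to later TB risk.

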An exploratory outcome for Aim 2 will be drug concentration (ng/mg) in a subset of small hair samples. Hair levels of INH measure long-term and cumulative exposure to INH will be used to determine if short-term increases in adherence translate to sustained changes in behavior.

Intervention-by-time-interaction. For Aims 1 and 2, we will check for the presence of intervention-by-time interaction by conducting separate analyses at months 3 and 6. We will use generalized estimating equations with an independent working correlation matrix for binary outcomes and random effect models for continuous outcomes.

Impact of COVID-related disruptions. Recruitment started on April 16 2018 and study activities were paused in March 19, 2020 due to a lockdown enforced by the Ugandan government in response to the COVID-19 pandemic. During this time, all research activities were stopped and participants on INH were contacted and instructed to stop taking their INH pills immediately, as there were no means to effectively monitor for liver toxicity. Study visits resumed on May 26, 2020 and enrollment resumed on June 16, 2020. We will conduct several descriptive statistics to examine to what extent the lockdown and the pandemic might have impacted the generalizability of the trial's findings. First, we will group the participants based on whether their scheduled INH completion date was before versus on or after March 19 2020 and will compare their baseline characteristics including measures of drinking. Second, we will perform an analysis to explore whether completion of INH before or after pandemic interruption acts as potential effect modifier of the incentive interventions.

Subgroup analyses. We will perform analyses to explore potential effect modifiers of the incentive interventions. For Aims 1 and 2, the potential moderators of interest are: sex, baseline level of alcohol use, time and risk preferences, and readiness to change . For each aim, we will fit separate models including 2-way interactions between randomization group and each potential effect moderator, as well as a model testing the interaction between the two

interventions. If an interaction is significant, subsequent stratified analyses will be conducted to explore the effect of the economic incentive interventions by categories of the moderator.

References

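### The COVID-19 analysis pools participants whose INH course spanned the lockdown with those enrolled after restart, so any effect of the interruption is diluted and cannot be separated from pandemic-era enrolment

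*SAP*

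**What the plan says.** All of this is in the SAP, Exploratory analyses, under Impact of COVID-related disruptions, unless stated otherwise.

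- Dates: "Recruitment started on April 16 2018 and study activities were paused in March 19, 2020". "Study visits resumed on May 26, 2020 and enrollment resumed on June 16, 2020".
- At the pause, "participants on INH were contacted and instructed to stop taking their INH pills immediately".
- Purpose: to examine "to what extent the lockdown and the pandemic might have impacted the generalizability" of the findings.
- Step 1: "we will group the participants based on whether their scheduled INH completion date was before versus on or after March 19 2020"; the two groups are then compared on baseline characteristics, including drinking.
- Step 2: an exploration of "whether completion of INH before or after pandemic interruption acts as potential effect modifier of the incentive interventions". This sentence says neither scheduled nor actual.
- Time allowed (SAP, Primary outcomes): "The participants were given up to 9 months to complete a 6-month (180-pill) INH preventive therapy course".

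No group is defined for participants who were on INH when the lockdown began.

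**The concern.** The purpose names two things, the lockdown and the pandemic, and they reached different people. Participants on INH on 19 March 2020 had their pills stopped and their visits suspended. Incentives are earned only at refill visits (Protocol 5.4.1 and 5.4.2), so this group could earn none until visits resumed. Some would also have had a 3- or 6-month visit fall due in the pause, and the drinking outcome needs both. Participants enrolled from 16 June 2020 had no such break, but joined during the pandemic. One before/after cut averages the two.

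At stake is the reading of step 2. A null result could hide a real loss of effect in the interrupted participants. A positive result could not be attributed to the interruption rather than to later enrolment.

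A smaller matter is that step 2 does not repeat the word scheduled. A scheduled date is fixed at enrolment. An actual completion date arises after randomisation and can be changed by the adherence incentive.

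**Working it through.** The documents give no figure for this analysis, so there is none to reproduce. The check is date arithmetic, followed by an illustration under stated assumptions.

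**Who falls in each group.** Take a 180-day course starting at enrolment.

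- 19 March 2020 − 180 days = 21 September 2019. The later group is therefore (a) those enrolled from about 21 September 2019 to 19 March 2020, a 180-day span, and (b) everyone enrolled from 16 June 2020.
- 19 March 2020 − 270 days = 23 June 2019. Those enrolled from about 23 June to 21 September 2019 are in the before group by schedule but were still inside the 9-month allowance at lockdown, so late-runners among them could also have been stopped.
- The pause in visits was 68 days (19 March to 26 May 2020); the pause in enrolment was 89 days.

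**Size of the groups.** Assume uniform accrual of 680 (Protocol 5.9.1) while enrolment was open. The end of enrolment is not given. I vary it from 30 September 2020 to 17 February 2022, the latter being six months before the SAP version date. Days open before 21 September 2019: 523. Days for (a): 180. Days for (b): D, from 16 June 2020 to the assumed end.

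- Number in (a) = 680 × 180 / (523 + 180 + D); number in (b) = 680 × D / (523 + 180 + D).
- Share of the later group that was interrupted: w = 180 / (180 + D).

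**Dilution.** Take the Aim 2 design effect of 12 points, 62% vs 50% (Protocol 5.9.2), in the before group and in (b), and zero in (a). The before/after contrast in the incentive effect is then 12 × w.

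**Power.** Use 612 evaluable participants, two-sided 5%, and the normal approximation for a difference between two risk differences, counting only the tail in the expected direction. The standard error is √(v/(n₁/2) + v/(n₂/2)), with v = 0.50×0.50 + 0.62×0.38 = 0.4856 in both groups as a simplification.

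| Assumed end of enrolment | D | (a) | (b) | w | Contrast, planned cut | Power, planned cut | Power, (a) vs all others, 12 points |
|---|---|---|---|---|---|---|---|
| 30 Sep 2020 | 106 | 151 | 89 | 0.63 | 7.6 | 14.6% | 24.0% |
| 31 Dec 2020 | 198 | 136 | 149 | 0.48 | 5.7 | 10.5% | 22.5% |
| 30 Jun 2021 | 379 | 113 | 238 | 0.32 | 3.9 | 7.0% | 20.1% |
| 17 Feb 2022 | 611 | 93 | 316 | 0.23 | 2.7 | 5.2% | 17.8% |

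First row in full: w = 180/286 = 0.629; contrast = 12 × 0.629 = 7.6; n₁ = 612 × 523/809 = 395.6; n₂ = 612 × 286/809 = 216.4; SE = 0.0833; power = Φ(0.0755/0.0833 − 1.96) = 14.6%.

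If the interruption removed only half the effect (6 points), the planned cut would show 6 × 0.23 to 6 × 0.63, about 1.4 to 3.8 points.

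**Separability.** In general the planned contrast is w × (loss in a) + (1 − w) × (loss in b), which is one number for two unknowns. With w = 0.476, a contrast of 5.7 points fits a 12-point loss in (a) alone, a loss of 5.7/0.524 = 10.9 points in (b) alone, or 5.7 points in both.

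**The before group.** The 90-day window from 23 June to 21 September 2019 holds 680 × 90/809 = 76 down to 680 × 90/1314 = 47 enrollees. Only those running late on 19 March 2020 would have been affected.

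**The case against.** The strongest reply is that the stated aim is generalisability under the lockdown and the pandemic together. A before/after split is a coarse but relevant answer to that, and isolating the INH stop is a further question. Step 1 only compares baseline characteristics, so the dilution argument does not apply to it. This is right as far as it goes. But the purpose names both, and one binary variable cannot distinguish them.

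Two stronger readings are tempting and are not supported.

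- A reader might infer that step 2 groups participants by actual completion and so breaks the randomised comparison. The text does not say actual. The natural reading is shorthand for the scheduled-date groups defined just before it, and a scheduled date cannot be altered by the incentive. What stands is that the wording leaves the variable open. If actual completion were used, the modifier would be a post-randomisation variable, and those who were stopped and never completed would have no category.
- A reader might infer that the analysis can show nothing about the interruption. A contrast reduced to 3–8 of 12 points is diluted and mixed, not empty.

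The size is also open to challenge. It rests on an assumed end of enrolment and on a total loss of effect, which the documents do not suggest. For Aim 2 the SAP measures adherence over the prescribed time when INH was stopped by instruction, and allows a 270-day window, which may absorb some of the pause; the SAP does not say how the pause enters either. For Aim 1 a sensitivity analysis already treats missed 3- or 6-month visits as heavy drinking. These points limit the illustration but do not touch the pooling.

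Finally, separating the interrupted participants raises power only to about 18–24%. That is true, and it argues for estimation over testing.

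**Conclusion.** The point holds in a limited form. The scheduled-date cut does place participants whose course spanned the lockdown with those enrolled after restart. If step 2 uses that cut, an effect of the interruption on the incentive effect is diluted and cannot be separated from pandemic-era enrolment. Under uniform accrual, interrupted participants would be about 23–63% of the later group, and a full 12-point loss among them would appear as about 3 to 8 points. Those figures are illustrative: the accrual pattern, the end date and the total loss of effect are all assumed, and some of the 93–151 counted as interrupted may already have stopped INH for other reasons. Step 2 is under-specified, not shown to be wrong. The analysis is exploratory and no primary or secondary result depends on it, so this is a cheap improvement.

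**What to change.** Change the SAP wording as follows.

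- Define three groups from enrolment date and scheduled INH end date: scheduled end before 19 March 2020; enrolled before 19 March 2020 with scheduled end on or after it; enrolled on or after 16 June 2020. The last two collapse back to the planned later group, so nothing is lost.
- Use this variable in both the baseline comparison and the effect-modifier model, and state that step 2 uses scheduled dates.
- Report the incentive effect in each group, and the differences between groups, with confidence intervals. Do not read a non-significant interaction as no impact.
- Add a sensitivity check for participants scheduled to finish before lockdown but still within the 9-month allowance on 19 March 2020, for example by moving them out of the before group. Defining that set by date (enrolled from about 23 June to 21 September 2019) keeps the grouping free of post-randomisation information.

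The cost is a few sentences and smaller groups in an exploratory analysis. The groups need only enrolment dates and scheduled end dates, and the primary analyses and significance levels do not change.
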